### 16.4.2 DBPCFC dosing schedule

This study includes three DBPCFCs: the first at Screening Visit 2, the second at 12 weeks, and the third at 52 weeks (end of treatment).

Each DBPCFC consists of two parts, active allergen (peanut) challenge and placebo challenge. Each challenge is to be performed on a separate day (Part 1 and Part 2). The active allergen challenge is either given on the first day or the second day. To ensure and preserve the double-blind nature of the challenge, independent (unblinded) study site staff need to prepare the material for each challenge prior to administration. Study staff/investigator administering the challenge and participants undergoing the challenge remain blinded to the identity of the

challenge on the two test days (i.e. if peanut allergen or placebo is tested on the first or the second day). The time interval between each challenge part is approximately **one to seven days**; there must be a minimum of one full day between Part 1 and Part 2 and maximum of 7 days. **There must be at least 24 hours between the completion of the OFC Part 2 and the first administration of study treatment at the Randomization visit.**

**At Part 1 (the first challenge day) of week 12 and week 52 visits, study treatment must be administered at least 1 hour before the DBPCFC.**

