### 16.4.4 Preparing for the food challenge

Prior to DBPCFC material preparation, independent **unblinded** study site personnel need to access the IRT system to obtain the allergen kit number to be used (corresponding to peanut allergen or placebo).

**IMPORTANT NOTE:** After **completion** of the 2nd day of the DBPCFC at Screening Visit 2 **ONLY**, the BLINDED site staff will access the IRT system to unblind the test and evaluate eligibility for randomization.

**This unblinding step is only applicable for the first DBPCFC at Screening and does NOT apply to the DBPCFC at weeks 12 and 52.**

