### 16.4.5 Evaluation parameters of the DBPCFC

Objective symptoms exhibited by participants should be evaluated through physical examination. Complaints arising from the participant without observable changes will be classified as subjective.

The DBPCFC will be considered **positive** with the occurrence of any dose-limiting symptom(s). Dose-limiting symptoms indicate a true allergic reaction occurring during administration of a single dose that should preclude the administration of any further doses in the view of the investigator. Investigators should refer to [Table 16-8](#) (CoFAR grading scale) for definition of dose-limiting symptoms. Symptoms can be mild, moderate or severe. Mild symptoms are not usually considered dose-limiting, although a combination of mild symptoms during a single dose might lead to the cessation of the OFC at the discretion of the investigator. All moderate and severe symptoms as defined in [Table 16-8](#) are considered dose-limiting.

Symptoms that require administration of any rescue medication (e.g. SABA, epinephrine or other) are considered dose-limiting symptoms. In this case, the challenge has to be stopped and the challenge is considered positive.

All findings that the investigator classifies as reactions to the DBPCFC should be recorded in source documentation and on a designated eCRF. These events should not be reported on the Adverse Event eCRF unless they constitute an SAE according to the investigator’s judgement.

The details and start time of any treatment and/or medication provided to treat DBPCFC-related allergic reactions should be recorded on the respective eCRF. The DBPCFC will be considered **negative** if a participant does not exhibit (a) dose-limiting symptom(s) (= positive challenge) at the end of the challenge.

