2.7.1 Adverse events (AEs)

Unless otherwise specified, summaries will include treatment-emergent adverse events (TEAEs) only. Treatment emergent adverse events are defined as events started after the first dose of study treatment and within 16 weeks after the last study treatment, or events present prior to the first dose of study treatment but increased in severity based on preferred term within 16 weeks after the last study treatment. All events that the investigator classifies as reactions associated to the DBPCFC or SPT will not be included in reporting of treatment-emergent AEs and may be reported separately. The number and percentage (with exact binomial 95% CIs) of participants with TEAEs will be summarized in the following ways:

- by treatment, primary system organ class and preferred term.
- by treatment, primary system organ class, preferred term and maximum severity.
- by treatment, Standardized MedDRA Query (SMQ) and preferred term.

Separate summaries will be provided for study treatment-related adverse events, death, serious adverse events, other significant adverse events leading to discontinuation and TEAEs with potential cause of accidental exposure or ingestion. If a participant reported more than one AE with the same preferred term, the AE with the greatest severity will be presented. If a participant reported more than one AE within the same primary system organ class, the participant will be counted only once with the greatest severity at the system organ class level, where applicable.

For the legal requirements of ClinicalTrials.gov and EudraCT, two required tables on TEAEs which are not SAEs with an incidence greater than a certain threshold based on the final database and on TESAEs and SAEs suspected to be related to study treatment will be provided by system organ class and PT on the safety set population.

If for a same patient, several consecutive AEs (irrespective of study treatment causality, seriousness and severity) occurred with the same SOC and PT:

- a. a single occurrence will be counted if there is ≤ 1 day gap between the end date of the preceding AE and the start date of the consecutive AE
- b. more than one occurrence will be counted if there is > 1 day gap between the end date of the preceding AE and the start date of the consecutive AE

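### A non-serious drug reaction misattributed to a placebo food challenge on the dosing day is kept out of the TEAE and hypersensitivity tables, and no other table is committed to show it

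*SAP*

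**What the plan says.** **Exclusion.** SAP 2.7.1 states: "All events that the investigator classifies as reactions associated to the DBPCFC or SPT will not be included in reporting of treatment-emergent AEs". The sentence ends by leaving separate reporting open: such events "will not be included in reporting of treatment-emergent AEs and may be reported separately". Protocol 12.5.2 carries the same exclusion and does not mention separate reporting. Neither text treats placebo-challenge days differently, and neither provides for review once the challenge order is known.

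**Timing.** Under Protocol 16.4.2, on Part 1 of the Week 12 and Week 52 visits "study treatment must be administered at least 1 hour before the DBPCFC". On order, "The active allergen challenge is either given on the first day or the second day". No study drug is given at Part 2, and "there must be a minimum of one full day between Part 1 and Part 2".

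**Blinding.** "Study staff/investigator administering the challenge and participants undergoing the challenge remain blinded" to which challenge is being given (Protocol 16.4.2). Sites learn the order at screening only: "This unblinding step is only applicable for the first DBPCFC at Screening" (Protocol 16.4.4).

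**Recording.** Challenge reactions go in source and on a designated eCRF. Of the adverse event form, Protocol 16.4.5 says: "These events should not be reported on the Adverse Event eCRF unless they constitute an SAE". Protocol 16.4.6 asks the investigator to judge whether a reaction comes from the challenge or from study drug. It requires a documented causality assessment for serious events.

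**Special interest.** The summary of adverse events of special interest (AESIs) in SAP 2.7.1.2, which includes hypersensitivity, covers treatment-emergent events only.

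**The concern.** The investigator has to separate a drug reaction from a challenge reaction without knowing whether any peanut was given. If the challenge that day was placebo, peanut cannot be the cause. The challenge order, once unblinded, would show this, but the exclusion rests on the blinded classification and nothing in the plan revisits it.

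Protocol 4.5 says the anaphylaxis risk known for the drug class theoretically applies to ligelizumab and asks investigators to be alert to it. Protocol 6.3.2 sets 2 hours of post-dose observation at Randomization and Weeks 4, 8, 16, 20 and 24. At Week 12 the challenge may begin after 1 hour, so it can start within a post-dose interval of that length. For the two arms that receive placebo for 8 weeks, Week 12 is only the second ligelizumab dose. At stake is the completeness of the tables a reader would consult for drug hypersensitivity.

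**Working it through.** The plan gives no figure for this point, so there is none to reproduce. The check traces where a reaction would be reported, then sizes the group in which the problem can arise.

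**Where a Week 12 Part 1 reaction goes**

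| Investigator's classification | Adverse event form | TEAE and hypersensitivity tables | Other planned output |
|---|---|---|---|
| Suspected drug reaction | Yes | Eligible | Usual AE outputs |
| Challenge reaction, serious | Yes | Excluded by the blanket wording | SAE reporting with causality; SAE table and listing named in SAP Table 2-2 |
| Challenge reaction, non-serious | No | Excluded | Optional only |

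The last row is the gap. The outputs in SAP Table 2-2 include no table of challenge reactions by peanut or placebo day. The symptom-severity endpoint covers peanut doses only. Epinephrine use during the challenge is summarised (SAP 2.4.2), with no stated split by challenge identity.

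**How many participants could be affected at Week 12**

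Inputs:
- Final sample size 211 (SAP 3).
- Randomization 2:2:2:2:1. All arms except the 16-week placebo arm are on ligelizumab by Week 12, so the share is 8/9 (Protocol 6.1.2).
- Dropout before Week 12 of 15% (SAP 3.1), varied from 0 to 25%.
- Share with the placebo challenge first: assumed 1/2, varied from 1/3 to 2/3. Protocol 16.4.3 says the sequence is randomly assigned but gives no ratio.

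Formula: sample size × ligelizumab share × (1 − dropout) × placebo-first share.

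- Central: 211 × 8/9 = 187.6; × 0.85 = 159.4; × 0.5 = 79.7, about **80**.
- Low: 187.6 × 0.75 × 1/3 = 46.9, about **47**.
- High: 187.6 × 1.00 × 2/3 = **125**.
- In one 46-participant ligelizumab arm: 46 × 0.85 × 0.5 = 19.6, about 20.
- In the 16-week placebo arm: 211 × 1/9 × 0.85 × 0.5 = 10.0, about 10.

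**What a few events would do**

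The event count here is hypothetical; the documents give none. With exact Clopper-Pearson intervals in an arm of 46, two reactions give 2/46 = 4.3% (95% CI 0.5% to 14.8%). If both are classified as challenge reactions, the table shows 0/46 = 0% (95% CI 0% to 7.7%).

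**The case against.** A reader might infer that drug hypersensitivity can disappear from the trial's safety data. The documents do not support that, for these reasons:

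- The data are kept, in source and on the designated eCRF.
- Serious reactions go on the adverse event form and are reported with a reasoned causality assessment.
- The exclusion applies only to events classified as challenge reactions, so a loss requires misattribution. Protocol 16.4.6 recognises the overlap and asks for a judgement. Protocol 10.1.1 asks investigators to enquire actively about hypersensitivity around both dosing and challenge.
- The DMC sees unblinded data, and anaphylaxis is adjudicated. Whether the adjudication search reaches the challenge eCRF is not stated, so complete loss is not shown.

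The scope is also narrow. Challenge and dosing coincide at 2 of 14 dosing visits. Under SAP 1.1, participants who had not completed Week 52 at the halt no longer undergo that challenge, so the issue is mainly Week 12. Part 2 days carry no dose. The Week 16 skin prick test precedes dosing, and later skin tests fall in the untreated follow-up.

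A reader might also take half of 211, about 105, as the number at risk of a masked drug reaction. That figure includes the 16-week placebo arm, who have had no ligelizumab by Week 12, and ignores dropout.

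All of this stands and limits the point. None of it commits the plan to a table in which a misattributed non-serious reaction on a Part 1 placebo day would be seen.

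**Conclusion.** The point holds in a limited form. A non-serious drug reaction misattributed to the challenge on a Part 1 placebo-challenge day is recorded, but it is left out of the TEAE and hypersensitivity AESI tables, and no planned output is bound to show it. This applies at Week 12 and, for the few who reach it, at the Week 52 challenge.

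The number of ligelizumab-treated participants exposed to this at Week 12 is about 80, within 47 to 125. It rests on the assumed dropout and an assumed challenge order. It is a count of opportunities; how many reactions occur, and how often they are misattributed, cannot be derived from the documents. The documents therefore do not support a claim that a known number of drug reactions is hidden, or that investigators will generally misattribute them.

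**What to change.** 1. In SAP 2.7.1, change *may* to *will* for separate reporting. After the challenge order is unblinded, tabulate reactions attributed to the challenge by randomized arm, Part 1 or Part 2, peanut or placebo challenge, and time since dosing.
2. Add a sensitivity TEAE table and a sensitivity hypersensitivity AESI table that count reactions on Part 1 placebo-challenge days, using the existing case retrieval search. Leave Part 2 placebo days out of this count, since no dose is given on them. The main TEAE tables keep the investigator's classification.
3. Record the change in SAP Section 4, because Protocol 12.5.2 has the same exclusion.

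The reactions are already collected and the challenge order is held in the IRT, so the cost is wording, programming and MedDRA coding of a few challenge eCRF entries. The eCRF is not in the documents, so confirm that it holds onset times before committing to time since dosing.

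The sensitivity tables will also count some nocebo reactions and reactions to the challenge matrix. These can be judged against the 16-week placebo arm, though only about 10 of its participants would have a placebo challenge on the dosing day.

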2.7.1.1 Exposure-Adjusted Incidence Rate

The crude incidence rate is defined as the percentage of participants with a specific adverse event divided by the total number of participants in each study group.

Due to expected differences in exposure and follow-up due to varied duration of study participation between participants, adverse event incidence rates will be provided as “exposure adjusted AE incidence rates” in addition to the crude incidence.

The EAIR is defined as the number of participants with a specific event divided by the total exposure-time among the participants in the study group. That is, the EAIR is calculated as:

$EAIR = n / \sum t_i$, where n is the number of participants having the i^{th} type event, and t_i is a participant's exposure time and defined as the shortest of the following:

1. time to the first episode of the i^{th} type event (if the event occurs),
2. time to the end of observation period, or
3. duration of study treatment plus the 16-week washout period (approximately corresponding to five half-lives) after last treatment dose

The total exposure time of all participants in a treatment group is $\sum t_i$. The EAIR is interpreted as the number of events occurring in a population per unit time. The exact Poisson 95% confidence interval for the EAIR will be provided as well, where an exact $100*(1-\alpha)\%$ confidence interval will be derived as follows (Garwood 1936, Sahai and Khurshid 1993):

- Lower confidence limit $L = \frac{0.5C_{\alpha/2,2n}}{\sum t_i}$ for $n>0$, 0 otherwise,
- Upper confidence limit $U = \frac{0.5C_{1-\alpha/2,2n+2}}{\sum t_i}$,

where $C_{\alpha,k}$ is the α th quantile of the Chi-square distribution with k degrees of freedom.

Whenever applicable, exposure adjusted incidence rates will be provided for the type as below:

1. TEAE: Primary SOC level, PT level

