2.7.1.2 Adverse events of special interest / grouping of AEs

AEs of special interest (AESI) are defined in the latest version of the compound electronic Case Retrieval Strategy (eCRS). The classification reflects the safety topics of interest identified in the current version of the QGE031 Development Safety Profiling Plan and may be updated based on review of accumulating data. The number and percentage of participants with treatment emergent AEs of special interest will be summarized by risk category, PT and treatment. The search criteria in the latest eCRS corresponding the MedDRA version at the database lock will be used and reported in the CSR:

- Hypersensitivity reactions (including anaphylaxis)
- Cardiovascular and Cerebrovascular (CCV) events
- Neoplastic conditions
- Injection site reactions
- Serum Sickness
- Eosinophilic Conditions / Churg-Strauss Syndrome
- Parasitic (Helminthic) infections
- Thrombocytopenia

Injection Site Reactions

For treatment emergent injection site reactions (ISR), besides the overall summary table for AESI, number of participants with recurrence of ISR (single ISR, 2-3 ISRs, > 3 ISRs) will be summarized by treatment.

Adjudicated AEs

From the AESIs listed above, the following AEs will be adjudicated by the independent committee. The adjudicated events will be listed, and a summary table may be provided following the adjudication.

- Anaphylaxis
- Cardiovascular and Cerebrovascular (CCV) events
- Neoplastic conditions

In addition, summaries will be provided by subgroups of age and allergy status (mono-sensitized and poly-sensitized).

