3.2.1 Precision for adverse events

Table 3-3 Precision levels (95% CI) for sensitivity of safety incidence rate for overall population

Event rate (proportion of participants with an event)	Number of participants	95% CI
0%	486	(0%, 0.8%)
1%	486	(0.3%, 2.3%)
2%	486	(1%, 3.7%)
0%	211	(0%, 1.7%)
1%	211	(0.1%, 3.5%)
2%	211	(0.6%, 4.9%)

4 Change to protocol specified analyses

On 31 March 2023, Novartis made a strategic decision to close recruitment in study CQGE031G12301 and terminate the study early. As a result, there are several changes to the specified analyses in the protocol, namely:

- Instead of 486 participants, the sample size is 211.

- There will be no recruitment of children under age 12, and the age-groups of interest are now 12-17 and 18-55.
- For participants who have reached Screening Visit 2 Part 1 and not completed Week 52 visit at the time of halt recruitment will need to complete Screening Visit 2 Part 2 to determine eligibility. If they are eligible, they will either continue treatment and perform assessments until Week 12 Part 2 or will stop treatment at the next scheduled visit if they have already completed Week 12 Part 2. This leads to limited number of participants reaching Week 52. Hence, non-inferiority test for sustainability of treatment effect at Week 52 compared to Week 12 is removed.
- Week 52 interim analysis will not be conducted.

There are also some changes made to simplify the analyses:

- Since the number of COVID-19 related intercurrent events is expected to be minimal, references to COVID-19 related intercurrent events were removed.
- Handling of intercurrent events for the secondary estimands were changed to be consistent with the primary estimand strategy.
- The two-dimensional tipping point analysis for the primary estimand was removed.

In analysis for primary estimand and secondary estimands(1, 2 and 4), log-transformed MTD at screening DBPCFC was added as covariate in logistic regression models.

The protocol mentions the summary measure of supplementary estimand is relative risk generated with a marginal standardization method. In SAP, relative risk is changed to risk difference to facilitate clinical interpretation.

5 Appendix

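### The exposure-adjusted rate is a first-event rate read as an event rate, and AESI risk categories in the Week 68 safety pool get only crude percentages

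*SAP*

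**What the plan says.** SAP 2.7.1.1 gives unequal length of participation as the reason for reporting an EAIR beside the crude incidence. The definition is: "The EAIR is defined as the number of participants with a specific event divided by the total exposure-time among the participants in the study group". In the formula, a participant's time ends at the earliest of the first episode, the end of observation, or "duration of study treatment plus the 16-week washout period (approximately corresponding to five half-lives) after last treatment dose". An exact Poisson interval is attached. The interpretation follows: "The EAIR is interpreted as the number of events occurring in a population per unit time".

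The scope is then fixed: "Whenever applicable, exposure adjusted incidence rates will be provided for the type as below". The list has one item, treatment-emergent adverse events (TEAEs) by primary system organ class (SOC) and by preferred term (PT).

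For AESI, SAP 2.7.1.2 says: "The number and percentage of participants with treatment emergent AEs of special interest will be summarized by risk category, PT and treatment". For injection site reactions it adds participant counts by number of reactions. SAP Table 2-2, which lists results that may be shown at the Primary Analysis, keeps the same split: exposure-adjusted tables for TEAEs, and a separate AESI row without adjustment.

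SAP 2.1.1.1 sets three safety pools: up to Week 8, up to Week 16, and the entire study up to Week 68. On the last of these, SAP Section 4 says of the early stop: "This leads to limited number of participants reaching Week 52".

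**The concern.** Two things do not fit together. First, participants with a first event over time to that event is a first-event rate. Calling it events per unit time invites a reader to take it as the frequency of episodes, which it is not when some participants have many episodes and others none. SAP 2.7.1.2 itself expects repeated injection site reactions.

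Second, the SAP adopts exposure adjustment because follow-up is unequal, then leaves it off the groupings chosen as the safety topics of interest. Protocol 12.8.2.1 expected every participant to have at least 9 months on ligelizumab, so crude percentages over the whole study could be read at face value. After the halt they depend heavily on when each participant was stopped. What is at stake is the absolute AESI risk reported for the Week 68 pool.

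**Working it through.** The SAP states no EAIR value, so there is none to reproduce. The nearest safety figures are the exact binomial intervals in SAP Table 3-3. For 211 participants, recomputation at 0%, 1% and 2% gives 0 to 1.73%, 0.13 to 3.46% and 0.57 to 4.93%, which agree with the table after rounding. They are intervals for crude proportions and take no account of follow-up.

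**1. What the formula estimates.** Let episodes occur at a mean rate m per year, with individual rates varying between participants (gamma distribution, variance k·m²). The chance of being event-free at time t is S(t) = (1 + k·m·t)^(−1/k), or exp(−m·t) when k = 0. Over follow-up T the EAIR is (1 − S(T)) divided by the integral of S from 0 to T.

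Example with m = 1 and k = 1: EAIR = [T/(1+T)] / ln(1+T).
- 28 weeks: T = 28/52.18 = 0.537, giving 0.349/0.430 = 0.81 per year.
- 68 weeks: T = 68/52.18 = 1.303, giving 0.566/0.834 = 0.68 per year.

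The true episode rate is 1 per year in both cases. The ratio of EAIR to episode rate, with m and k assumed, is:

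| m per year | k | 28 weeks | 68 weeks |
|---|---|---|---|
| any | 0 | 1.00 | 1.00 |
| 0.2 | 1 | 0.95 | 0.89 |
| 1 | 1 | 0.81 | 0.68 |
| 1 | 2 | 0.69 | 0.53 |
| 2 | 1 | 0.71 | 0.56 |
| 2 | 2 | 0.56 | 0.40 |

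The SAP's reading is exact with no clustering (k = 0), close for rare events, and too low for frequent, clustered ones.

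**2. Planned follow-up in the Week 68 pool** (table in SAP 1.1, counted from Day 1).
- Randomized but short of Week 12 Part 2 at the halt (Group 3): 12 + 16 = 28 weeks.
- Already past Week 52 (Group 1): 52 + 16 = 68 weeks.
- Stopped at the next visit after Week 12 (Group 2): in between.

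The range is 68/28 = 2.4-fold.

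**3. Effect on a crude AESI percentage.** With constant hazard λ, the crude percentage is 1 − exp(−λ·T). The documents give no AESI rate, so λ is assumed over a range.

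| λ per year | 28 weeks | 68 weeks | Ratio | EAIR at either length |
|---|---|---|---|---|
| 0.05 | 2.6% | 6.3% | 6.3/2.6 = 2.4 | 0.05 |
| 0.1 | 5.2% | 12.2% | 12.2/5.2 = 2.3 | 0.1 |
| 0.2 | 10.2% | 22.9% | 22.9/10.2 = 2.2 | 0.2 |

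The pooled percentage lies between the two columns. If one third of participants had 28, 48 and 68 weeks each (an assumption), λ = 0.1 would show as (5.2 + 8.8 + 12.2)/3 = 8.7%. The true mix is not in the documents.

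**4. Whether the PT-level rates fill the gap.** They do not. A participant with two PTs in one risk category is counted once in each PT rate, and each PT has its own clock. The category rate needs that participant once, with time ending at the earlier event. It has to be computed from participant data and cannot be obtained by adding PT rates.

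**The case against.** The strongest reply is that nothing computed would be wrong. The numerator, the stopping of time and the exact Poisson interval belong together as a first-event rate, and only the interpretation sentence is loose. That stands. A reader might infer that the formula or its interval is faulty, but the definitions in SAP 2.7.1.1 do not support this.

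Second, AESI are TEAEs, so each AESI preferred term already receives an EAIR. This also stands, and it narrows the gap to the risk-category level. A reader might infer that AESI get no exposure adjustment at all, which would be too strong. The sentence introducing the EAIR speaks of adverse event rates in general and could be taken to cover AESI categories, but the one-item list and Table 2-2 point the other way.

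Third, a reader might infer a biased comparison between doses. The documents do not support that. The Week 68 pool sets the combined 240 mg arms against the combined 120 mg arms, and randomization should give both a similar mix of follow-up. The Week 8 and Week 16 pools, which carry the placebo comparison, have short and nearly equal windows.

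Fourth, recurrence is partly covered by the planned counts of single, 2-3 and more than 3 injection site reactions. It is tempting to size the understatement for these reactions from the 28.6% in Protocol 4.5. That figure pools four asthma regimens, three of them dosed every two weeks, and the documents do not say how many reactions each participant had. No firm factor follows from it.

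**Conclusion.** The point holds in a limited form. The interpretation sentence does not match the definition; it is right only without clustering of events within participants. For frequent, clustered events the EAIR was 40% to 81% of the episode rate, under assumed rates of 1 to 2 per year and k of 1 to 2. The more useful finding is that AESI risk categories have no exposure-adjusted rate in the one pool where follow-up differs widely. There the same hazard gives crude percentages about 2.2- to 2.4-fold apart between 28 and 68 weeks, for assumed constant hazards of 0.05 to 0.2 per year. The actual pooled shortfall cannot be calculated without the distribution of follow-up.

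The consequence is confined to absolute AESI risk in the Week 68 pool and to setting it beside other pools or studies. No efficacy result, placebo-controlled safety comparison or dose comparison is shown to change. This is an inexpensive improvement to safety reporting.

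**What to change.** In SAP 2.7.1.1:

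- Replace the interpretation sentence with: the EAIR is the number of participants with a first event per unit of time at risk.
- Add a second item to the list, *AESI: risk category level*, with the same exact Poisson interval, for the entire-study pool. Time for each participant ends at the first event of any PT in the category.
- At the same time, tidy the crude-rate definition, which as worded divides a percentage by the number of participants again. SAP 2.7.1 and 2.7.1.2 already state the working summary correctly as number and percentage, so this is clerical.

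EAIRs for serious adverse events, and all-episode rates for injection site and accidental-exposure reactions, are optional.

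The cost is a few lines of text and reuse of the same program on more groupings. The downside is wide intervals for rare AESI, which would reflect how little information there is.
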